**Study Sites:**

Multicenter study with sites in North America, Australia, Europe, and Argentina.

**Planned Number of Participants:**

All participants who have completed the planned treatment period in the parent study, AL002-2, are invited to participate in this LTE study. Enrollment is optional and participation may be offered at the discretion of the Investigator.

**Participant Selection:**

Eligibility for study inclusion will be limited to participants who completed the planned treatment period in the parent study AL002-2. Participants must consent to this AL002-LTE study and complete all outstanding assessments from AL002-2 prior to Day 1/Week 1 of the AL002-LTE study.

**Criteria for Inclusion and Exclusion:**

**Inclusion Criteria**

Each participant must meet all of the following criteria to be enrolled in this study:

1. The participant has completed the planned treatment period in the AL002-2 study. Completion of the planned treatment period is defined as any participant who did not prematurely and permanently discontinue the study drug in the AL002-2 study.
2. The participant is willing and able to give informed consent. Where local regulations permit inclusion of participants deemed not able to provide informed consent, a legally authorized representative must provide informed consent on his or her behalf, and the participant must provide assent, in accordance with the local regulations, guidelines, and institutional review board or independent ethics committee.
3. Female participants must be nonpregnant and nonlactating, and 1 of the following conditions must apply:
  - a. Participant is not a woman of childbearing potential (WOCBP) (either surgically sterilized, or physiologically incapable of becoming pregnant, or at least 1-year postmenopausal [amenorrhea duration of 12 consecutive months with no identified cause other than menopause]).

- b. Participant is a WOCBP and agrees to use an acceptable contraceptive method from screening until 12 weeks after the last dose of study drug. Acceptable contraception is defined as using hormonal contraceptives or an intrauterine device combined with at least 1 of the following forms of contraception: a diaphragm or cervical cap, or a condom, or the sole sexual partner to a vasectomized male. Vasectomized males must have received medical assessment of surgical success. In addition, total abstinence, in accordance with the lifestyle of the participant, is acceptable.
    - c. A WOCBP must have a serum pregnancy test conducted at screening. Additional requirements for pregnancy testing during and after study intervention are described in the Schedules of Assessments.
  4. Male participants must agree to use acceptable contraception and not donate sperm from screening until 12 weeks after the last dose of study drug. Acceptable contraception for the male participant when having sexual intercourse with a WOCBP who is not currently pregnant is defined as using a condom. In addition, WOCBP partners must use hormonal contraceptives or an intrauterine device. Vasectomized male participants should have received medical assessment of surgical success.
  5. Participant weighs  $\leq 120$  kg; body mass index (BMI) is between 18.5 and 34.9 kg/m^2 inclusive.
  6. The participant has availability of a person (“study partner”) who, in the Investigator’s opinion, has frequent and sufficient contact with the participant (eg, at least 10 hours per week of in person contact), is able to provide accurate information regarding the participant’s cognitive and functional abilities, agrees to provide information at clinic visits (which require partner input for scale completion), and signs the necessary consent form.
    - a. The study partner must have sufficient cognitive capacity, in the Investigator’s opinion, to accurately report upon the participant’s behavior, cognitive, and functional abilities. The study partner should be in sufficiently good general health, in the Investigator’s opinion, to have a high likelihood of maintaining the same level of interaction with the participant and participation in study procedures throughout the study duration.
    - b. Every effort should be made to have the same study partner participate throughout the duration of the study, and to have the same study partner as in the parent study.
  7. The participant and study partner are fluent in the language of the tests used at the study site as assessed by site personnel.
  8. The participant is willing and able to complete all aspects of the study (including MRI). The participant should be capable of completing assessments either alone or with the help of the study partner. Participants whose disease has progressed such that they cannot complete the efficacy assessments may participate in the study for assessment of safety.
  9. The participant has adequate visual and auditory acuity, in the Investigator’s opinion, sufficient to perform the neuropsychological testing (corrective lenses and hearing aids are permitted).
  10. Participant agrees not to donate blood or blood products for transfusion for the duration of the study and for 1 year after the final dose of study drug.

*Inclusion criteria for participants in the optional Tau PET imaging assessment with [F]MK-6240 only:*

11. Participant has not had excessive radiation exposure prior to enrollment in the trial, as defined by local standards.
12. [F]MK-6240 is available to the PET imaging center based on manufacturing distribution network and local regulations.

*Inclusion criteria for participants in the optional longitudinal Amyloid PET imaging assessment only:*

13. Participant has not had excessive radiation exposure prior to enrollment in the trial, as defined by local standards.
14. An approved amyloid radiotracer is available to the PET imaging center based on manufacturing distribution network and local regulations.

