An ET Visit is performed only in cases where the participant is prematurely discontinued from the study for any reason. If the participant withdraws or is discontinued from the study for any reason, the ET must be completed no longer than 4 to 8 weeks after the last administered dose. All safety evaluations, efficacy, biomarker, PK and ADA assessments must be completed at this visit. See [Table 9](#) footnotes for additional information.

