### **3.2.4.      **End of Study/Week 57 Visit****

Participants are considered to have completed the study if they engage in all procedures and visits as outlined in [Table 9](#). The EOS Visit is defined as the final study visit at Week 57 which is 8 weeks after the last AL002 administration.

All outstanding assessments will be completed within the specified timepoints as indicated in [Table 9](#). For a detailed list of procedures, please refer to [Table 9](#).

No additional care is expected to be required for participants after participation in the AL002-LTE study has ended because of their participation in this clinical trial.

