### **6.3.1. Adverse Events, Adverse Events of Special Interest, and Serious Adverse Events**

All AEs, AESIs, and SAEs must be collected and recorded, regardless of cause or relationship to AL002, after the participant signs the ICF until the end of study participation.

The following AEs and special situations must also be reported to Alector Drug Safety within 24 hours of awareness:

- AEs assessed as *related* to the *radiopharmaceutical* Neuraceq® (florbetaben F18 injection). **Please note:** *if the site's imaging facility is located outside of the institutional facility, please ensure the imaging lab is aware of this requirement.*
- Special situations (overdose, off-label use, abuse, misuse, occupational exposure, medication error) associated with Neuraceq® **or** the Alector study drug regardless of whether the special situation is associated with an AE and *regardless of the Investigator's causality assessment of the event with respect to the radiopharmaceutical or the Alector product.*

Any unresolved or ongoing AEs, AESIs, and SAEs will be collected and recorded up through resolution, stabilization, or return to baseline. Additionally, SAEs considered related to study drug or radiotracer, which occur at any time during the study, will be followed until resolution, participant withdrawal of consent, loss to follow-up, or death. Additional details of AE collection are provided in [Section 7](#).

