### **7.13.2. Pregnancy**

If applicable, pregnancy tests are to be performed at screening/baseline and/or at Week 49 and/or at EOS/ET (see Schedule of Assessments [Table 9](#)). Female participants must be instructed to discontinue all study drugs and inform the Investigator immediately if they become pregnant during the study.

The Investigator must report any pregnancy within 24 hours of becoming aware of it using the paper Pregnancy Report Form. Follow-up information documenting the pregnancy outcome should be reported on the paper Pregnancy Report Form. The site should email the Pregnancy Report Form to [[contact]](mailto:[contact]), according to the instructions provided in the Study Specific Regulatory Binder.

The participant must be immediately discontinued from study drug and/or PET imaging procedure. An uncomplicated pregnancy will not be considered an AE or SAE, but all pregnancies will be followed until a final outcome is known.

Pregnancies are captured if they occur in female participants or in the sexual partners of male participants from the time the participant is first exposed to the study drug or radiotracer until the final study visit.

Any congenital abnormalities associated with a pregnancy that occurred during study participation are considered SAEs. The outcome of any pregnancy and complete health information regarding the fetus will be recorded in the source documentation and reported to Pharmacovigilance.

Any SAE occurring in association with a pregnancy must be reported to Pharmacovigilance regardless of whether the events are considered related to study drug.

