2. STUDY OBJECTIVES AND ENDPOINTS

The study objectives and endpoints are provided in [Table 2-1](#).

Table 2-1. Study Objectives, Endpoints and Estimands for LTE

| Primary Objectives | Primary Safety Endpoints and Primary Estimand |
|--|---|
| 
To evaluate the long-term safety and tolerability of AL002 in participants with AD.
 | 
Part 1: Primary Safety Endpoint and Estimand:
 
 • Treatment condition: Group T-T (AL002 15 mg/kg, 40 mg/kg or 60 mg/kg IV Q4W) continues their Core Study treatment in the LTE Study; Group P-TC treated with Placebo in the Core study will be titrated to 60 mg/kg of AL002 in the LTE study. • Target population: adult participants with AD excluding apolipoprotein E (APOE) epsilon 4 (e4)-homozygous (e4/e4) participants. • Primary endpoints: AESI incidence and SAE incidence over all weeks. • Accounting for intercurrent events: a composite strategy will be used to handle intercurrent events as below: 
 ○ Hypothetical strategy for handling premature study drug discontinuation for any reason (AEs with a start date more than 90 days after study drug discontinuation are not counted) ○ Treatment policy strategy for handling all other intercurrent events. • Population-level summaries: the descriptive statistical summaries for each treatment group of incidence rates for all AESIs and SAEs over similar periods of time. 
Part 2: Primary Safety Endpoints:
 
 • Changes from baseline (CFBs) in vital signs, physical findings, neurological findings, ophthalmological findings, ECG findings, and clinical laboratory results. • MRI abnormalities (ARIA events) • C-SSRS. 
Primary Estimand for Safety Endpoints Above:
 
The estimand for the Part 2 endpoints is defined with similar attributes as for the Part 1 estimand except applied to the different endpoints
 |

| Primary Objectives | Primary Safety Endpoints and Primary Estimand |
|--|---|

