6.2.2.1 Treatment-Emergent Adverse Events

6.2.2.1.1 *Treatment-Emergent Adverse Events for Placebo Data*

For the Placebo Data as specified in Section 3.2, the treatment-emergent AEs (TEAEs) are defined the same way as in the Core Study SAP. And handling of incomplete dates is specified in the Core Study SAP.

6.2.2.1.2 *Treatment-Emergent Adverse Events for AL002 Dosed Participants*

For participants who were ever exposed to AL002, AEs that occur on or after the first dose date of AL002 and up to 90 days after study drug discontinuation will be considered TEAEs.

- If both the start time of the AE and the time of the first AL002 administration are available, an AE is considered a treatment-emergent AE (TEAE) if its start date and time are on or after the first AL002 administration and no later than 90 days after the last dose date of AL002. The last dose date of AL002 is defined in Section 3.2.
- If either the start time of the AE or the time of the first AL002 administration is unavailable, an AE is considered a TEAE if its start date is on or after the first dose date of AL002 and no later than 90 days after the last dose date of AL002. Handling of incomplete dates is specified in Section 6.2.2.6.

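### Pregnancy reporting ends at the final visit, 28 to 56 days before the protocol's own 12-week contraception period ends; LTE follow-up also stops short of the SAP's 90-day counting limit

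*Protocol*

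**What the plan says.** **Contraception.** Under Protocol Section 4.1, criterion 3b, a woman of childbearing potential "agrees to use an acceptable contraceptive method from screening until 12 weeks after the last dose of study drug". Under criterion 4, men must use contraception and "not donate sperm from screening until 12 weeks after the last dose of study drug".

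**Pregnancy reporting.** Section 7.13.2 captures pregnancies in female participants and in male participants' partners "from the time the participant is first exposed to the study drug or radiotracer until the final study visit". Tests are listed at screening/baseline, Week 49 and EOS/ET, with none later.

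**Final visit.** For completers it is the "final study visit at Week 57 which is 8 weeks after the last AL002 administration" (Section 3.2.4). Participants who stop the drug are withdrawn from the study (Sections 4.3.1 and 4.3.2), and for them "the ET must be completed no longer than 4 to 8 weeks after the last administered dose" (Synopsis; Section 3.2.5). The ET visit ends participation (Section 3.2.2). After a withdrawal related to an adverse event, Section 3.2.5 defers it until the event resolves.

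**Adverse events.** AEs, AESIs and SAEs are recorded "after the participant signs the ICF until the end of study participation" (Section 6.3.1). After follow-up ends, Section 7.9 still requires reporting of related SAEs that the investigator learns of.

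**SAP.** Events on or after the first AL002 dose and "up to 90 days after study drug discontinuation will be considered TEAEs" (Section 6.2.2.1.2). In the primary safety estimand of Table 2-1, "AEs with a start date more than 90 days after study drug discontinuation are not counted".

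**The concern.** The protocol sets a post-dose period during which pregnancy is to be avoided, then stops collecting pregnancies part of the way through it. Section 7.9 does not fill the gap: it covers related SAEs only, and Section 7.13.2 says that an uncomplicated pregnancy is neither an AE nor an SAE. Information on exposed pregnancies, in participants or partners, could be lost in the weeks the protocol itself marks out.

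The second issue is one of ascertainment. The SAP accepts events up to day 90 after the last dose, but the LTE schedules no contact after EOS or ET. New non-serious AEs, new AESIs and unrelated SAEs that start between the final visit and day 90 would count if known, yet nothing systematically collects them. A reader of an overall incidence percentage could take it as covering 90 days off drug when the observed period is shorter and differs between completers and early leavers.

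**Working it through.** **1. Reproduce the plan's 8 weeks.** Dosing every 4 weeks from Week 1 to Week 49 gives (49 − 1)/4 + 1 = 13 doses, which agrees with SAP Section 6.2.1. The last dose is at Week 49 and EOS at Week 57: (57 − 49) × 7 = 56 days, or 8 weeks. The SAP target days agree: LTE Week 56 (Day 393) minus LTE Week 48 (Day 337) = 56 days.

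**2. Compare the end of capture with the two limits.** Contraception period: 12 × 7 = 84 days. SAP limit: 90 days. If capture ends d days after the last dose, the uncovered time is 84 − d or 90 − d.

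| Final visit | d | 84 − d | share of 84 | 90 − d | share of 90 |
|---|---|---|---|---|---|
| EOS, on target | 56 | 28 | 33% | 34 | 38% |
| EOS, 5 days early | 51 | 33 | 39% | 39 | 43% |
| EOS, 5 days late | 61 | 23 | 27% | 29 | 32% |
| ET at 4 weeks | 28 | 56 | 67% | 62 | 69% |
| ET at 8 weeks | 56 | 28 | 33% | 34 | 38% |

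The ±5 days is the visit window in the schedule header (Table 9), taken here to apply to EOS. Four weeks is the lower reading of an ambiguous ET phrase that sets no clear minimum. In every scheduled case both limits outlast capture. An ET deferred for an unresolved event is the exception.

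**3. Put the 90-day gap on the scale of the primary endpoints.** Table 2-1 defines AESI and SAE incidence over all weeks, so the denominator is the whole counting window, not only the time after the last dose.

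- Completer, LTE window only: 34/(337 + 90) = 34/427 = 8.0%.
- Completer continuing an active dose, integrated window (last dose at target Day 1037): 34/(1037 + 90) = 34/1127 = 3.0%.
- Early leaver, LTE window only, last dose on LTE Day D and ET at 4 weeks: 62/(D + 90). As an illustration, D = 113 (LTE Week 16) gives 62/203 = 31%.

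These are shares of time, not of events.

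**4. See where the SAP allows for shorter follow-up.** In Section 7.4.3, by-interval denominators use the earlier of the last participation day and last dose plus 90 days. In Section 7.4.8, Kaplan-Meier curves for ARIA censor participants without an event at the earliest of last MRI, death, and last dose plus 90 days. No such allowance is stated for the overall incidence percentages, although Table 2-1 asks for rates over comparable lengths of time.

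**The case against.** The strongest reply concerns the SAP. Ninety days is a ceiling for counting, not a promise to observe. Section 7.1.1.2.1 treats it the same way, listing later safety data without summarising them. The ceiling also serves the integrated analysis, which includes parent-study participants who never entered the LTE; the parent study's follow-up length is not given, so a gap can be shown only for LTE participants. This stands. A reader might infer that the primary safety estimand claims 90 days of observation and fails to deliver it, or that the documents contradict each other. They do not: a ceiling that follow-up does not reach means incomplete ascertainment.

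A reader might also infer that 38% to 69% of post-treatment events, or of primary-endpoint events, are missed. Those figures are uncovered time after the last dose. Turning them into shares of post-treatment events needs a constant hazard, which sits badly with the pattern Protocol Section 1.4 describes for anti-amyloid trials (more ARIA early, less with continued dosing). For a completer the gap is 8% of the LTE window.

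Nor is coverage necessarily shortest in those who stop for safety. ET is deferred after an AE-related withdrawal, unresolved events of any cause are followed (Sections 7.7.1 and 7.9), and new ARIA requires repeat MRI until resolved or stable (Section 7.11.2). The gap concerns new-onset events after the final visit.

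On pregnancy, conceptions recognised by the final visit are captured and followed to outcome. Read generously, Section 7.13.2 also reaches a conception before that visit that is recognised later, although no contact is scheduled at which it would surface. This narrows the gap but does not close it.

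**Conclusion.** The pregnancy mismatch holds. Reporting stops about 28 days (EOS) to 56 days (earliest ET) before the 84-day contraception period ends, and Section 7.9 provides no route for an uncomplicated pregnancy first recognised in that interval. The documents give no count of women of childbearing potential or of male participants with such partners; that few pregnancies are expected is an assumption about this population. The point is therefore one of safety reporting and consistency, not of numbers. Which post-dose period is clinically right is not judged here.

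The secondary point holds as incomplete ascertainment in the LTE: 34 days short of the SAP's ceiling at EOS and up to 62 days at the earliest ET. It affects the reading of overall incidence percentages, most of all for participants who leave early without a deferred ET. It does not invalidate the primary safety estimand.

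**What to change.** **Protocol Section 7.13.2.** Reconcile it with criteria 3b and 4 so that the pregnancy reporting period, for participants and male participants' partners, covers the protocol's own post-dose contraception period. This is a one-sentence change to reporting and does not alter treatment.

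**SAP.** State beside the TEAE definition and the Table 2-1 estimand that 90 days is a counting ceiling and that LTE ascertainment of new events ends at EOS/ET. Report observed post-dose follow-up by treatment group next to the overall incidence tables. This costs a sentence and a small table. It changes no result, but shows what the percentages cover.

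**Optional.** Add one scripted contact near day 90 for new AEs, SAEs and pregnancy. It costs one call per participant, plus edits to Table 9 and to the definitions of end of participation and end of study (Sections 3.2.2 and 12.2). It would not detect asymptomatic imaging AESIs, because ARIA is determined by central MRI reading (Section 7.6.4), so the SAP statement is needed with or without it.

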### **Exclusion Criteria**

Participants are excluded who meet any of the following exclusion criteria:

1. Participants deemed not able to provide consent or assent by the Investigator or by local regulations.
2. Participants who were prematurely and permanently discontinued from treatment in the parent study for safety reasons.
3. The participant has MRI evidence of:
  - a. >2 lacunar infarcts.
  - b. Any territorial infarct >1 cm^3.
  - c. White matter hyperintense lesions on the FLAIR sequence that correspond to an overall Fazekas score of 3.
  - d. Participants who have an increase in their number of microbleeds, since the previous screening/ baseline MRI in the AL002-2 study and >5, should be discussed with the Medical Monitor.
  - e. Participants who have developed ARIA-E and ARIA-H in the parent study and who were permitted to continue dosing according to the ARIA management guidelines, will not be excluded from participation in the AL002-LTE, on the basis of microbleeds or hemosiderosis.
4. Anticoagulant medications other than antiplatelet agents are prohibited within 90 days of screening and throughout the study. Short-term use of anticoagulants to treat an emergent medical need is permitted. Treatment with platelet anti-aggregation agents such as aspirin, clopidogrel, or dipyridamole is permitted.
5. Participants taking any passive immunotherapy (eg, immunoglobulin) or other long-acting biologic agent that is under evaluation or approved to prevent or postpone cognitive decline.
6. Participation in the AL002-LTE is deemed inappropriate for any reason per Investigator discretion.
7. Participant agrees not to receive any investigational treatment, other than AL002, during the study.

### **Clinical Outcome Assessments – Neurocognitive and Functional Tests:**

The following neurocognitive and functional tests (described in [Section 14.2](#)) will be performed according to the guidelines set forth in the Site Rater Manual. Neurocognitive and functional tests will be performed prior to study drug administration (if applicable) and prior to any stressful procedures (eg, blood collections, LPs, imaging). Blood collection can be considered a stressful procedure for a participant, according to the Investigator's clinical judgment.

- Clinical Dementia Rating (CDR®)
- Mini-Mental Status Examination (MMSE)
- Repeatable Battery for the Assessment of Neuropsychological Status – Update (RBANS-Update)
- Alzheimer's Disease Assessment Scale-Cognitive Subscale (ADAS-Cog13)

- Alzheimer’s Disease Cooperative Study-Activities of Daily Living – Mild Cognitive Impairment Scale (ADCS-ADL-MCI)

If a participant is taking intermittent or short-term regimens of medications known to impair consciousness or cognition, such medication must be stopped 2 days or 5 half-lives (whichever is longer) prior to any cognitive or behavioral assessment. Use of cannabinoids (other than cannabidiol) is prohibited within 72 hours prior to any cognitive or behavioral assessment.

